#### **ADDITIONAL PRINCIPLES FOR MEDICAL RESEARCH COMBINED WITH MEDICAL CARE.**

The physician may combine medical research with medical care, only to the extent that the research is justified by its potential prophylactic, diagnostic or therapeutic value. When medical research is combined with medical care, additional standards apply to protect the patients who are research subjects.

The benefits, risks, burdens and effectiveness of a new method should be tested against those of the best current prophylactic, diagnostic and therapeutic methods. This does not exclude the use of placebo, or no treatment, in studies where no proven prophylactic, diagnostic or therapeutic method exists.

At the conclusion of the study, every patient entered into the study should be assured of access to the best-proven prophylactic, diagnostic and therapeutic methods identified by the study.

The physician should fully inform the patient which aspects of the care are related to the research. The refusal of a patient to participate in a study must never interfere with the patient-physician relationship. In the treatment of a patient, where proven prophylactic, diagnostic and therapeutic methods do not exist or have been ineffective, the physician, with informed consent from the patient, must be free to use unproven or new prophylactic, diagnostic and therapeutic measures, if in the physician's judgment it offers hope of saving life, re-establishing health or

alleviating suffering. Where possible, these measures should be made the object of research, designed to evaluate their safety and efficacy. In all cases, new information should be recorded and, where appropriate, published. The other relevant guidelines of this Declaration should be followed.

### Revision History

SAP Version Number	Supersedes	Reason for revision (If applicable)	Revised by (If applicable)

## LIST OF ABBREVIATIONS

Abbreviation	Definition
AE	Adverse event
ALT	Alanine aminotransferase
AP	Alkaline phosphatase
AST	Aspartate aminotransferase
AUC	Area under the curve
AUC 30min	Area under the curve from minute 0 to minute 30
AUC 60min	Area under the curve from minute 0 to minute 60
AUC 120min	Area under the curve from minute 0 to minute 120
AUC t	Area under the curve from 0 hours to the last measureable concentration
AUC inf	Area under the curve extrapolated to infinity
BMI	Body Mass Index
BP	Blood pressure
BSAP	Bone specific alkaline phosphate
C	Celsius
CBC	Complete blood count
C t	Concentration at time t
CFR	Code of Federal Regulations
CM	Concomitant medication
cm 	Centimeter squared
C max	Maximum observed plasma concentrations
CPK	Creatinine phosphokinase
CRF	Case report form
dL	Deciliter
ECG	Electrocardiogram
EDTA	Ethylenediaminetetraacetic acid
F	Fahrenheit
GCP	Good Clinical Practice
GGT	gamma glutamyl transpeptidase
H	Hour
HCl	Hydrochloride
HRT	Hormone replacement therapy
ICF	Informed consent form
ICH	International Conference on Harmonisation
IEC	Independent Ethics Committee
IM	Intramuscular
IRB	Institutional Review Board
IV	Intravenous
J	Joules

Abbreviation	Definition
k	Apparent elimination rate constant
kg	Kilogram
KIU	Kilo international units
µg	Microgram
L	Liter
LDH	Lactate dehydrogenase
LOCF	Last observation carry forward
µm	Micrometer
mL	Milliliters
mmol	millimole(s)
NSAID	Nonsteroidal anti-inflammatory drug
OCT	Optical Coherence Tomography
PD	Pharmacodynamics
PE	Physical examination
PK	Pharmacokinetics
PPI	Proton pump inhibitors
PRSPB	Bruising
PTH	Parathyroid hormone
SAE	Serious adverse event
SC	Subcutaneous
SD	Standard deviation
t ½	Apparent half life
TEAE	Treatment-emergent adverse event
TGA	Therapeutic Goods Administration
T max	Time to maximum concentration
ZP	Zosano Pharma
M207	Zosano intracutaneous microneedle system containing zolmitriptan

## **1.0 Introduction**

This statistical analysis plan (SAP) is intended to give a detailed description of the summaries and the analyses for the study. The analyses outlined in this document are designed in support of clinical protocol CP-2018-002.

- This Statistical Analysis Plan (SAP) should be finalized prior to database lock, final analysis of pharmacokinetics and before the treatment codes are applied to the analysis data.
- The Statistical analysis will be initiated after completion of impact assessment of protocol deviation.

## **2.0 Study Title**

A randomized open-label four-way crossover study to compare the pharmacokinetics, safety, and tolerability of M207 3.8 mg (administered as two 1.9 mg patches) at two different application locations (upper arm and thigh) for 30 minutes with intranasal zolmitriptan 2.5 mg and 1 hour wear time (upper arm) in healthy volunteers

## **3.0 Study Objectives**

1. To compare the pharmacokinetics, safety and tolerability of M207 3.8 mg administered to either the upper arm or thigh, particularly with respect to skin irritation (erythema, edema, bruising, bleeding)
2. To compare the pharmacokinetics, safety and tolerability of M207 3.8 mg worn for either 30 minutes or 1 hour on the upper arm
3. To compare the pharmacokinetics, safety and tolerability of M207 3.8 mg to intranasal zolmitriptan 2.5 mg

## **4.0 Study Description**

### **4.1 Randomization and Blinding**

The 24 subjects are planned to receive each of the four treatments (A, B, C, D) 48 hours apart.

The order of receiving of the investigational products for each subject will be determined according to a randomization schedule which will be appropriate to the study design. Subjects will be randomized to one of the four sequences: either ABCD or BDAC or CADB or DCBA. Equal allocation of the sequence will be ensured.

The randomization schedule will be generated using SAS® statistical software (Version: 9.4; SAS Institute Inc, USA), by a biostatistician of Clianza Research Limited. The randomization schedule will be maintained under controlled access.

The personnel involved in the dispensing of investigational products will be accountable for ensuring compliance to randomization schedule.

At the end of each dosing day, the safety data from the subjects will be evaluated. If tolerability is deemed to be acceptable by the Principal Investigator, a decision will be made to proceed to the next dosing day.

#### **4.2 Pharmacokinetic Variables**

Serial blood sampling PK assessments will be performed at 0.00 (pre-dose), 2, 5, 10, 15, 20, 30, 45, 60, 90 min, 2 hr, 4 hr, 8 hr, 12 hr and 24 hr post dose for each treatment period.

Concentrations of zolmitriptan and its metabolite n-desmethyl zolmitriptan in plasma will be measured for the formulations using a validated assay.

Based on the concentration data below pharmacokinetic parameters will be calculated using Phoenix® WinNonlin® professional software (Version 6.4 or higher).

**Pharmacokinetic Parameters:** Cmax, Tmax, AUCt, AUCi, AUC(0-30mins), AUC(0-60mins), AUC(0-120mins), Kel, Tmax, tHalf and AUC\_%Extrap\_obs.

#### **4.3 Safety Assessment**

The safety of zolmitriptan 2.5 mg and M207 3.8 mg patch will be assessed on the basis of:

- 1) Vital signs monitoring
- 2) Adverse Events (AEs) monitoring
- 3) Clinical laboratory tests
- 4) Physical examinations
- 5) ECG
- 6) Concomitant medications
- 7) Investigator visual skin assessment

#### **4.4 Sample Size**

No formal sample size calculation was performed. In previous studies of Zosano Pharma transdermal products in healthy volunteers, a sample size of 24 was sufficient to provide directional information on tolerability, as well as adequate information on pharmacokinetics, and comparative pharmacokinetics for various regimens.

## 4.5 Study Design, Treatment and Plan

This is a single-center, open-label, randomized, four-way crossover study. Each subject will receive each of the four study treatments once, followed by in-clinic monitoring and extensive blood sample collection for pharmacokinetic analysis.

Dosing will occur approximately 48 hours apart, until completion of dosing in randomized order per the treatment sequence tables. Plasma samples from the dosing days will be sent to the analytical laboratory for analysis and tolerability for each of the dose levels will be summarized.

After completion of the four dosing days, subjects will be assessed one final time and dismissed from the study.

### **Investigational Products:**

#### **M207 Intracutaneous Microneedle System**

The Zosano M207 Intracutaneous Microneedle System is a novel drug delivery technology which consists of a disposable titanium patch centered on an adhesive backing with microneedles that are dry-coated with the drug product formulation, and a reusable handheld applicator that ensures that the patch is applied with a defined application speed and energy to the site of administration.

M207 systems consist of zolmitriptan coated titanium array with an adhesive backing that is applied using proprietary patch applicators. Descriptions of the 1.9 mg patches used in the study are described below.

#### **Zolmitriptan Nasal Spray**

Zolmitriptan nasal spray is a commercially available product (Zomig® Nasal Spray) and will be purchased for use in this study. The dose used in this study will be 2.5 mg/0.1 ml. This dose should be administered to either the right or left nostril with the subject's head tilted slightly backward.

#### **M207 1.9 mg**

The M207 1.9 mg consists of a 3 cm^2 titanium array of microprojections that are nominally 340 µm in length coated with 1.9 mg of zolmitriptan. The array is applied to the center of a 5 cm^2 tan adhesive patch. The patch is attached to the interior of a white to off-white polycarbonate ring co-molded with a desiccant, packaged in a cup.

Study treatments are:

**Treatment A:** M207 3.8 mg administered as two 1.9 mg patches, 30 min wear time (upper arm application)

**Treatment B:** M207 3.8 mg administered as two 1.9 mg patches, 30 min wear time (thigh application)

**Treatment C:** M207 3.8 mg administered as two 1.9 mg patches, 1 hour wear time (upper arm application)

**Treatment D:** Intranasal zolmitriptan 2.5mg

#### **4.6 Subject Population**

The study population will consist of 24 healthy volunteers (12 women and 12 men) 18 to 50 years of age in general good health.

#### **4.7 Number of Subjects**

A sufficient number of subjects will be enrolled to ensure application of 24 healthy subjects.

#### **4.8 Study Duration**

Screening is 1 day (up to 30 days prior to dosing); in-clinic duration of study participation for each subject is approximately 2 weeks total (includes 4 treatment periods), and the final end of study visit occurs on one day.

#### **4.9 Withdrawal/Discontinuation Criteria**

The Participation in the study is completely voluntary and a subject can choose to withdraw from the study at any time. In addition, a subject can be withdrawn for any of the following reasons: the Principal Investigator decides that continuing the drug may be harmful, a subject is non-compliant with the protocol, a subject has a serious reaction to the treatment, or the study is stopped by the Independent Ethics Committee, US Food and Drug Administration (FDA), or Zosano Pharma.

In order to complete all treatments for each dose, additional subjects may be enrolled to account for subjects who withdraw or are discontinued from the study. If a subject does not complete all planned treatments, the reason and date of withdrawal from the study must be recorded in the CRF. Zosano Pharma should be notified immediately if a subject withdraws prematurely from the study.

## **5.0 Endpoints**

### **5.1 Safety and Tolerability**

- Incidence of adverse events
- Change in physical examination findings from pre-dose to 12 hours post-dose
- Changes in vital signs from pre-dose to 10 min, 60 min, 2 hour, 4 hour, and 12 hour post-dose
- Changes in ECG parameters from pre-dose to 15 min, 60 min, 8 hour, and 12 hour post-dose
- Scores from an investigator visual skin assessment for erythema, edema, bruising and bleeding at the patch application sites from pre-dose to 30 min (for 30 min wear time treatment assignments only), 60 min (for 60 min wear time treatment assignment only), 12 hour and 24 hour post-dose
- Changes in clinical labs from screening to end of study
- Patch adhesion score at time of application at 30 min and 60 min post-dose (for 60 min wear time treatment assignment only)

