#### **6.4 End of Study Visit/or Early Termination**

- Within 48 hours after completion of all protocol required procedures on the last dosing day, subjects will complete an End of Study Visit. At that time, the following assessments will be performed:
- Record all AEs, whether observed by investigator, reported by the subject, observed in laboratory findings, or discovered by other means, on the AE CRF through the end of study final visit.
- Record a 12-Lead ECG
- Record any new concomitant medications and adverse events
- Measure vital signs (inclusive of temperature)
- Perform a physical examination
- Measure body weight
- Investigator visual skin assessment of the application sites
- Collect blood and urine for laboratory tests and serum pregnancy test (for all females)
- Dismiss subject from the study

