### 7.3 Assessment Details

#### 7.3.1 Clinical Laboratory Tests

Standard clinical laboratory tests (serum pregnancy for all women, CBC, hematology, and urinalysis) will be performed at Screening and End of Study (or early termination) and urine pregnancy testing for all women at each Admission/baseline visit.

A blood sample at screening will be taken to perform serological tests for HIV, Hepatitis B and Hepatitis C.

CBC will include the following: Hematocrit, hemoglobin, red blood cell count, white blood cell count with differential, platelets, mean corpuscular volume, mean corpuscular hemoglobin, and mean corpuscular hemoglobin concentration.

Blood hematology will include the following: Urea, glucose, aspartate aminotransferase (AST), alanine aminotransferase (ALT), alkaline phosphatase (AP), lactate dehydrogenase (LDH), sodium, phosphate, potassium, chloride, creatinine phosphokinase (CPK), globulin, cholesterol, creatinine, serum calcium, total bilirubin, triglyceride, cholesterol (HDL and LDL), gamma glutamyl transpeptidase (GGT) and uric acid.

Urinalysis will include the following: bilirubin, blood, glucose, ketones, leuokocyte esterase, nitrite, pH, protein, specific gravity, and urobilinogen. Microscopic examination will be conducted if protein, leukocyte esterase, nitrite and/or blood are detected.

Urine drug screen and alcohol (breath) testing will be performed at screening and each Admission/baseline visit. Urine drug screen will test for amphetamine, barbituates, cocaine, cannabinoids, phencyclidine (PCP), opioids, and methamphetamines.

Samples will be analyzed by a local laboratory. After reviewing the laboratory reports and evaluating the results, the Investigator must review, sign/date the laboratory report.

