### **16.0 Safety Analyses**

Safety analyses will be performed on safety population set (refer section 6.2). All safety data will be listed by subject, treatment group and parameter, separate listings of all abnormal laboratory findings will be provided, and clinically significant abnormalities will be recorded as AEs.

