## **16.2 Vital Signs**

Descriptive summaries of actual values and changes from pre-dose to 10 min, 60 min (1 hr), 120 min, 240 min (4 hr), and 720 minutes (12 hr) post-dose will be calculated for heart rate, systolic blood pressure, and diastolic blood pressure and presented by treatment group.

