## **16.5 Clinical Laboratory Evaluations**

Clinical laboratory values will be displayed in data listings, including a listing of all abnormal results. Clinically significant values will be flagged.

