**Listing 16.2.8.1: Listing Abnormal Clinically Significant Lab Results**

Subject	Visit	Date	Laboratory Test	Units	Range	Results	Abnormality Flag
XXXX							

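### The SAP names laboratory change as a safety endpoint but summarises none, and a laboratory AE first found at the final sample is tabulated under the last treatment received

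*SAP*

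**What the plan says.** **Endpoint.** SAP 5.1 includes "Changes in clinical labs from screening to end of study" among the safety and tolerability endpoints. The corresponding list in Protocol 4.2 has no laboratory item.

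**Analysis.** SAP 16.5 reads: "Clinical laboratory values will be displayed in data listings, including a listing of all abnormal results. Clinically significant values will be flagged". Protocol 10.5 likewise plans listings of abnormal laboratory findings and no summary. For vital signs, by contrast, SAP 16.2 plans "Descriptive summaries of actual values and changes from pre-dose", and SAP 16.3 does the same for ECG.

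**Shells.** The SAP contents show no laboratory summary table. Apart from the drug-screen and pregnancy listings, the one laboratory results shell is Listing 16.2.8.1, titled "Listing Abnormal Clinically Significant Lab Results".

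**Sampling.** Protocol 7.3.1 says that the standard tests "will be performed at Screening and End of Study (or early termination"). Protocol 6.4 places the end-of-study visit "Within 48 hours after completion of all protocol required procedures on the last dosing day".

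**Route into the AE tables.** SAP 16.0 says that "clinically significant abnormalities will be recorded as AEs". SAP 16.1 assigns each AE, by its date and time, to the latest dose before it. Summary Tables 14.3.1.1 to 14.3.1.4 have columns for A to D and no overall column.

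**Sequences.** SAP 4.1 gives ABCD, BDAC, CADB and DCBA with equal allocation of 24 subjects.

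**The concern.** There are two linked problems.

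First, an endpoint worded as a change has no method behind it. Someone programming from the SAP would produce listings and would have no instruction to compute or summarise a change for any analyte. A modest shift across the group would then have to be found by reading individual values. Haemoglobin is an example: 360 mL of PK and discard blood is drawn between the two laboratory samples.

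Second, the only route by which a laboratory finding reaches a summary table is as an AE, and the AE tables are by treatment. With one scheduled post-dose sample per subject, a finding first seen there cannot be tied to one of several treatments from the laboratory data alone, yet the rule gives it a treatment label. The study's objectives are to compare safety between arm and thigh, between wear times, and between M207 and the nasal spray, so the label could be read as evidence in those comparisons.

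**Working it through.** The documents state no figure for this endpoint, so there is nothing to reproduce. The check sets the sections side by side and then counts.

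**1. Is the endpoint derived anywhere?** Of the quantitative endpoints that SAP 5.1 words as changes, vital signs and ECG have change summaries (16.2, 16.3) and laboratory tests do not (16.5). Listing 16.2.8.1 covers clinically significant abnormal results only; 16.5 asks for all values and all abnormal results.

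**2. Which treatment is last in completers?** Equal allocation gives 24/4 = 6 subjects per sequence.

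| Sequence | Subjects | Fourth treatment |
|---|---|---|
| ABCD | 6 | D |
| BDAC | 6 | C |
| CADB | 6 | B |
| DCBA | 6 | A |

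Each treatment is last in 6 of 24 subjects. With 24 dosed per treatment, a column can show at most 6/24 = 25% from laboratory AEs first found at end of study, even if every completer is affected. In the ABCD group all such events go to the nasal spray, after three M207 doses.

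**3. How is an overall rate diluted?** If k completers have such a finding, the all-subjects rate is k/24 and the average column shows (k/4)/24. For an assumed k = 4, that is 4/24 = 16.7% overall against 1/24 = 4.2% per column on average.

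**4. What share would be filed under another treatment?** Suppose one treatment causes the abnormality. Let p1 to p4 be the chance that an effect of a dose in period 1 to 4 is still present at the final sample. Each treatment occupies each period in 6 subjects, so

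share filed elsewhere = (p1 + p2 + p3) / (p1 + p2 + p3 + p4).

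- Full persistence (all p = 1): 3/4 = 75%, that is 18 of 24 if all completers are affected.
- Only period 3 and 4 effects still present (p1 = p2 = 0, p3 = p4 = 1): 1/2 = 50%.
- Only period 4 effects still present: 0%.

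**5. Is persistence a strong assumption?** Take exact 48-hour spacing, last-day procedures ending at 24 h, and a visit 0 to 48 h later.

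| Dose | Hours before final sample |
|---|---|
| 4 | 24 to 72 |
| 3 | 72 to 120 |
| 2 | 120 to 168 |
| 1 | 168 to 216 |

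Earlier doses are several days further back, so the share depends heavily on how fast an effect resolves. The documents give no laboratory event rate or time course.

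**The case against.** The strongest case against is that listings are adequate for laboratory data in a 24-subject descriptive Phase 1 study with no formal sample size calculation, and that SAP 16.5 does what Protocol 10.5 asks. On this view the added bullet in SAP 5.1 is the outlier, and AE Listing 16.2.7 already shows period, dosing time and onset, so a reader could see that a laboratory AE arose after the last dose. Much of this stands. It limits the seriousness, and rewording the SAP 5.1 bullet would also close the endpoint mismatch. It does not remove the label in the summary tables, and the SAP's permission to add or modify shells specifies no method.

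Four stronger readings are tempting, and the documents do not support them:

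- *That shifts below clinical significance go unreported.* SAP 16.0 and 16.5 promise listings of all values. The gap is that change is not summarised, and that the shell is narrower than the text.
- *That laboratory AEs can fall only under the fourth treatment.* Early terminators are sampled when they stop, so their AE goes to whichever treatment was last. Protocol 8.1 also allows an unscheduled serum sample after a clinically important AE.
- *That a single-treatment label is always wrong.* SAP 16.1 attributes by when the event occurred. Where symptoms or an unscheduled sample date the onset to one period, the label follows the rule properly.
- *That three quarters of laboratory AEs will be misfiled.* That is the full-persistence case with a single causal treatment, not a forecast.

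It may also be asked why laboratory AEs should differ from physical-examination findings, which are also collected at end of study. The examination is repeated 12 hours after every dose, so each period has its own observation; the laboratory tests have none between periods.

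**Conclusion.** The point holds and should be corrected, as a narrow matter of specification and labelling. The SAP names a laboratory change endpoint that it does not summarise and that Protocol 4.2 does not list. For clinically significant abnormalities first detected at the final scheduled sample, after more than one treatment and with no documented earlier onset, the AE rule supplies a treatment label that two samples per subject cannot support.

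In size, at most 6 of 24 completers can contribute such an AE to any one column. The share filed under a treatment other than the cause runs from 0% to 75%. That range assumes all 24 complete with equal allocation, one causal treatment, and an effect no more likely to be present at the final sample after an earlier dose than after the fourth. The upper end requires full persistence.

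**What to change.** 1. **SAP 16.5:** add a table for the Safety Population, all subjects combined and not by treatment, giving the screening value, end-of-study value and change for each quantitative analyte (n, mean, SD, median, minimum, maximum), plus a low/normal/high shift table.
2. **SAP 16.1:** state that laboratory AEs first detected at the end-of-study or early-termination sample after more than one treatment, with no documented onset in a specific period, appear in an overall column headed as not attributable to a single treatment. A flag to the same effect in the by-treatment tables would also serve and leaves the standard layout intact.
3. **Listing 16.2.8.1:** widen it to all abnormal values with the significant ones flagged, as 16.5 already says.
4. **Protocol 4.2 and SAP 5.1:** reconcile the two endpoint lists. If the sponsor decides that laboratory change is not an endpoint, the SAP 5.1 bullet should say what is actually planned; item 2 is needed either way.

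The cost is SAP wording and two extra tables from data already collected, with no new samples or procedures. The small downside is that these AEs no longer carry an unqualified treatment label.
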